2.3.3 ASSESSMENT OF POTENTIAL RISKS AND BENEFITS

Minimizing Risk 1.

Several strategies are being proposed to help minimize the risk of worsening of symptoms, or to increase the potential to avert emergent crises or quickly detect an adverse event if one should occur:

- Recruitment and consent procedures are expected to help minimize this potential impact. For example, from the outset of each study, prospective participants will be informed by the intake counselor (or member of the research team) about the study and the likely possibility that the treatment will focus on suicidal risk, so they will be less likely to be surprised later by the content of the treatment. This aspect will be reinforced again during the informed consent process.
- Counselor participants will be self-selected based on their experience and interest in working with suicidality in a hybrid teletherapy/in-person format. Not all counselors are skilled and comfortable dealing with suicidal risk, so having counselors who are willing to work with this population and who are not afraid of discussing suicidal thoughts and behaviors, or dealing with potential crisis situations, will greatly increase the quality of care and the likelihood of counselors responding appropriately to imminent suicidal ideation (should it occur), including discerning the waxing and waning typical of suicidality from actual worsening of symptoms.
- Counselor participants will be extensively trained to conduct CAMS and CC-DBT via online/in-person training and consultation. Online and in-person training will be conducted by experts in CAMS and CC-DBT and ongoing expert consultation will address any concerns regarding worsening or lack of improvement in symptoms in a particular participant. Additionally, each CCC has a weekly staff or case management meeting to discuss any cases giving rise to safety concerns—thus this will be available for discussion of TAU treatments.
- All treatments provided as part of the study will allow for the possibility of increasing the frequency of sessions should a particular client need more support for a period of time. It is quite common in clinical care to add an extra session when the client is struggling. [Note: All CCC contacts with a student client are documented in the student's CCC treatment file. Therefore, dosage of treatment will be monitored.]
- Several procedures at the participating CCCs, although called by different names, are geared toward addressing crises and detecting adverse events early in the process (although study participants will receive unique treatments and complete research assessments, they will also be treated as regular clinic clients—one of the “effectiveness-based elements” of this study): 1) Students in crisis, regardless of who the counselor is, can contact the CCC at any time during business hours and receive crisis management as needed. 2) All clients are given the number to a 24-hour Crisis Call hotline and the Crisis Text Line. 3) The CCCs are part of University-wide teams that seek, with students' permission, to help students who are involved with multiple departments

campus-wide (e.g., financial aid, judicial affairs, counseling, campus police, disability resource services) and this allows counselors to more effectively help manage certain crisis situations (e.g., students often become suicidal because of loss of financial aid and access to information through the financial aid officer on the team may help prevent a suicidal crisis).

- Because of the remote nature of teletherapy care, student's current location as well as emergency contact numbers for third party involvement (e.g., parents or roommates approved by the client) will be obtained for each client should there be a worsening of symptoms.
- There will also be an understanding of secondary, even tertiary, backup methods for reconnecting with clients should there be technological issues or an unstable internet connection.
- As is routinely done in conventional clinical trials, student participants who worsen significantly may be removed from the study if this is deemed to be in the clinical interests of the student participant (e.g., a student participant may need to withdraw from school to pursue a higher level of care). This is often done in collaborative discussions between student participant and counselor.
- Project Coordinators (PCs), PIs, Co-Is, and consultants will be available for consultation with the participating counselors on a regular basis. Additionally, the PIs or Co-Is in charge of clinical supervision will be available as needed for consultation regarding safety concerns, regardless of current condition assignment, to all participating counselors.
- The NIMH Data Safety and Monitoring Board (DSMB) will monitor all adverse events on a regular basis.

Minimizing Risk 2.

Breach of confidentiality, including unauthorized access to digital data. Several precautions will be taken to protect the confidentiality and privacy of participants from being violated, including unauthorized access to digital data. Risk will be minimized as follows:

- All online clinical care across the four research sites will be provided via videoconferencing on platforms that are fully HIPAA compliant, such as HIPAA-compliant Zoom.
- At the beginning of each session, counselors will make sure that the client is in a secure location where other family members or friends may not be able to listen in on teletherapy sessions. Clients may need to use headphones as part of the effort to minimize what others might hear of any teletherapy session.
- Confidentiality and the limits to confidentiality will be discussed with participants and stated in the informed consent.
- A concern of college student participants might be the release of information about mental health to their academic departments or their families. We will assure participants in the informed consent that we will be unable to disclose this type of information to anyone outside the CCC, unless the student participant has signed a release of information or one of the limits of confidentiality applies. However, we will

explain that even if one of the limits applies (e.g., imminent suicidality), we will make every attempt to discuss this with the client first and only those who absolutely need to know will be informed (e.g., their parents or a roommate if they live in an off-campus apartment). As part of the assessment process, we will collect emergency contact information (parent or other trusted family member/emergency contact adult's name and phone number) and we will also discuss conditions under which a parent or guardian, or this emergency contact person, may be notified for assistance in case of an emergency. Such conditions may include situations such as: the student participant is imminently suicidal and/or is perceived as a danger to themselves or others but does not agree to a safety plan or has missed/cancelled appointments and their commitment to safety cannot be confirmed. Counselors will review these crisis management strategies with student participants during their first therapy session. This aspect is particularly important given the remote nature of teletherapy.

- *Unique ID:* Participants will be assigned a unique study ID and a GUID (Global Unique Identifier) to be used in the completion of all online questionnaires. The individual's name and identifying personal information will not be maintained in computer files that can be accessed via the same system. The GUID is a universal subject ID allowing researchers to share data specific to a study participant without exposing personally identifiable information (PII) and match participants across studies.
- *Security of computers and networking hardware:* The Duke University Medical Center (DUMC) servers hosting the REDCap data repositories are connected to the Duke internal network and protected by the Duke Health Enterprise firewall; access to the repositories is permitted only through properly authenticated web application programming interfaces. REDCap data are encrypted both at rest and in transit. The DUMC database-hosting infrastructure has been audited by the Duke Information Security Office for compliance with HIPAA and Duke Health data security policies. Procedures are in place for rapid recovery from hardware or database failure. All telehealth delivery will be conducted on fully HIPAA-compliant teleconferencing platforms.
- *User authentication/roles:* User access to the REDCap web portal relies on a centrally managed list of users within the Duke Data Center (DDC), their authentication credentials, and their roles and access privileges. The REDCap platform used in the current study will leverage the Duke Health Enterprise authentication system. The DDC will manage user access groups and will provide granular control over specific access permissions, depending on study role (e.g., PC, RA), to specific aspects of the portal, such as eCRFs or study management functions. Password complexity and expiration rules are managed by the Duke ISO to ensure compliance. Usernames will be set for periodic review to make sure that changes to staff roles are audited jointly with the PIs.
- *Security of transmitted data:* All self-report measures will be collected using a secure online survey program relying on SSL (Secure Sockets Layer) encryption such as REDCap or Qualtrics. This technology guarantees the privacy of all data transferred between the participant and data center and assures visitors that the site they are accessing is authentic. To initiate this secure connection, the IEs will register each participant into

the REDCap system, entering their unique study ID, and then ask him/her to complete the self-report measures. For subsequent assessments conducted remotely, the IE will email a unique link to the participant for completing the self-report measures.

- The only individuals who will have access to any information linking participant names to participant codes will be the Principal Investigators (PIs), Project Coordinators (PCs), Independent Evaluators (IEs), Research Assistants (RAs) and, if needed, an overseeing ethical body (IRB or DSMB). Others will only have access to first names (e.g., the PIs while doing case consultations) or the GUID. Moreover, all data published in reports or articles will be described in aggregate form.

Minimizing Risk 3.

Emotional distress associated with assessments. Although studies show that asking about suicidal ideation does not increase the risk of suicidal behavior,^{152,30} it is possible that assessments may increase emotional distress. Therefore, the following precautions will be taken:

- The assessments across timepoints will be conducted by well-trained IEs with experience treating suicidal individuals. Assessments of suicidal risk will primarily occur in interview formats (e.g., SSI, SITBI), so the IE conducting the assessments can respond appropriately if the participant becomes emotionally dysregulated. The interview-based assessments will also use validation strategies to ensure that participants feel supported.
- Standard policies (e.g., obtaining current address and an emergency contact) will be developed to manage suicide risk when evaluated remotely.
- Assessments will be limited to those domains essential to conducting the evaluation of treatment response and acceptability.
- The total time spent completing interviews/questionnaires for the CAMPUS Trial for student participants will be 2-3 minutes a week and between 60-180 minutes at baseline and between 45-120 minutes at the middle of Stage 1, the end of Stage 1, the middle of Stage 2, the end of Stage 2, and 3-month follow-up, depending on the assessment timepoint and the student participants' responses to the interview questions (an affirmative answer to a question on suicidality/self-injury/ suicide attempt(s) results in follow-up questions).
- Finally, and importantly, to ascertain the safety of participants during/after scheduled assessments, the IEs will rely on the commonly utilized University of Washington Risk Assessment Protocol (UWRAP).¹¹⁰ This protocol will guide the IEs through a series of questions and strategies to help ensure that participants are safe prior to ending the assessment session.

Minimizing Risk 4.

Being involuntarily hospitalized. The following precautions will be taken to avoid involuntary hospitalizations:

- When student participants indicate that they are imminently suicidal and are not able/willing to take steps to guarantee they will not hurt themselves, the potential scenarios for voluntary vs. involuntary hospitalization will be discussed in detail.
- Every option for voluntary hospitalization will be explored. In the case of an online assessment or therapy session, these options will also be coordinated with the help of a third party. Often, students will agree to go to the hospital on a voluntary basis. Sometimes, suggesting that they call a friend or a family member who will go with them to the emergency room helps them decide to go voluntarily.
- Consultation with a parent/other trusted family member/emergency contact adult will be explored with the student participant as well.

Minimizing Risk 5.

Feeling coerced to participate in the study. Although this is unlikely to occur based on our experience (plenty of students decline research participation!), the following precautions will be taken:

- Intake counselors and/or members of the research team will describe the study to students who seem interested in hearing about it. They may say something like, "We are currently conducting a study here to help students who may be struggling with suicidality. Would you like to hear more about it?" If a student says no directly or indirectly, the intake counselor will end this discussion and move on to other treatment options.
- The intake counselor will clarify that, "There are other options for treatment. The study is just one of them."
- During the consent process, the member of the research team will ensure that there is enough time for questions and discussion before a student signs the consent form.
- The PI or the PC will make themselves available throughout the study to consult with the participant and/or his/her counselor if there are any concerns about the student participant continuing to participate.
- It will be made very clear both by the intake counselor and by the research staff that participation is voluntary and that declining to participate will have absolutely no impact on the student's ability to receive services at the CCC, now or in the future.

3 OBJECTIVES AND ENDPOINTS

Table 2 provides a summary of the objectives, endpoints, and justification for the endpoints for the CAMPUS Trial that will be conducted immediately following the feasibility study. A more detailed description of the measures can be found in Section 8.1.

Table 2. CAMPUS Trial Objectives, Endpoints, and Justification

Objectives	Endpoints	Justification for Endpoints
Primary Aims of the CAMPUS Trial		
Suicide-Related Behaviors Aim 1: To compare four pre-specified ATSSs in terms of primary and secondary	Scale for Suicidal Ideation (SSI)	The primary outcomes will be reduction in suicidal risk (SR; suicidal ideation primarily but also non-suicidal self-

Table 2. CAMPUS Trial Objectives, Endpoints, and Justification		
Objectives	Endpoints	Justification for Endpoints

outcomes. Hypothesis 1: The ATS that begins with CAMS and then augments with DBT for insufficient responders will be more effective in reducing SR than the other ATSs.
 
Aim 2: To determine whether a suicide-focused first-line intervention (e.g., CAMS) produces greater reductions in SR than a non-suicide focused one (e.g., TAU). Hypothesis 2: ATSs that begin with CAMS will be more effective in reducing SR than those beginning with TAU.
 
Aim 3: To determine whether providing a comprehensive suicide-focused approach (e.g., CC-DBT) among insufficient responders to Stage 1 treatments will be more effective in reducing SR than a less intensive suicide-focused approach (e.g., CAMS). Hypothesis 3: Adding CC-DBT at Stage 2 with insufficient responders to Stage 1 will be more effective in reducing SR compared to adding or continuing CAMS at Stage 2.
	Self-Injurious Thoughts and Behaviors Interview (SITBI)	
injury, suicide attempts, and suicides) at the end of Stage 1, Stage 2, and at 3-month follow-up.
 
Recognizing that measurement of suicide-related behaviors is fraught with challenges,¹¹² we are defining SR as “suicidal ideation, attitudes, behaviors and plans which take into account severity, intent, and ability to cope with ideation without engaging in suicidal behaviors, such as planning/rehearsal, non-suicidal self-injury (NSSI), suicide attempts (SAs), and suicide.” Our primary assessment measures for SR are two interviews to measure suicidal ideation (SI; defined as self-reported thoughts of suicide-related behavior) and suicidal behaviors, including suicide attempts and NSSI. Suicides will also be tallied.

Secondary Aims of the CAMPUS Trial: Functioning		
Functioning – Relevant to Aims 1-3 described above and Aims 4-5 described below.	
Counseling Center Assessment of Psychological Symptoms (CCAPS-62 or CCAPS-34).
 
Clinical Global Impression for Severity (CGI-S) and Improvement (CGI-I).
	Secondary outcome measures will be overall distress, depression, social and generalized anxiety, substance abuse, eating concerns, academic functioning, clinical global impressions by participants and assessors of severity and improvement in suicidal risk.
Secondary Aims of the CAMPUS Trial: Mediation		

Aim 4: To evaluate treatment-specific mediators of change. Hypothesis 4a: Treatment effects in CAMS, relative to TAU, will be mediated by improvement in suicide-focused processes, including suicidal cognitions, suicide-focused attentional bias, and hopelessness. Hypothesis 4b: Treatment effects in DBT, relative to Stage 2 CAMS, will be mediated by increased emotion regulation, self-efficacy for managing emotions, and improved skills.
	
The Difficulties in Emotion Regulation Scale (DERS)
 
The DBT-Ways of Coping Check List (DBT-WCCL)
 
The Acceptance and Action Questionnaire II (AAQ-II)
	The measures listed include those found in previous studies to mediate outcome in CC-DBT and CAMS.

Table 2. CAMPUS Trial Objectives, Endpoints, and Justification		
Objectives	Endpoints	Justification for Endpoints
	The Suicide Cognitions Scale (SCS) The Optimism Hope Scale (OHS) PROMIS Self-Efficacy for Managing Emotions	
Secondary Aims of the CAMPUS Trial: Moderation		
Aim 5: To evaluate whether (1) number of lifetime suicide attempts (SAs), ³¹ (2) Borderline Personality Disorder (BPD) features, ³² (3) baseline distress, ³³ (4) sexual and gender minority (SGM) self-identification, ^{18,19} and (5) comorbid substance and alcohol abuse affect, predict or moderate treatment response.	History of previous suicide attempts (SITBI) The Personality Assessment Inventory – Borderline Features Scale (PAI-BOR) The Optimism Hope Scale (OHS) The Global Assessment Scale (GAS) Sexual orientation and gender identity Alcohol Use Disorders Identification Test (AUDIT) and Drug Abuse Screening Test (DAST)	Aim 5 pertains to the identification of predictors and moderators of treatment response, which could be incorporated as secondary tailoring variables in later studies or during dissemination. Potential predictors and moderators were gleaned from the suicidology literature and/or from CC-DBT and CAMS.
Hypothesis 5a: Student participants with >2 prior SAs, ³¹ more BPD features, ³² and SGM (self-identified) ³⁴ will be less responsive to Stage 1 treatments. Hypothesis 5b: Student participants with >2 prior SAs, high baseline distress, more BPD features, and SGM (self-identified) ^{18,19} will be more likely to respond to CC-DBT than to CAMS in Stage 2.		
Tertiary/Exploratory Aims of the CAMPUS Trial: Implementation and Process		
Aim 6: To evaluate the ATSSs in CCC settings, we will assess implementation outcomes outlined by Proctor ³⁵ employing the Quality Implementation Framework (QIF). ³⁶ A mixed-methods process evaluation will be conducted with CCC stakeholders to identify facilitators/barriers to implementation and sustainability.	The Client Satisfaction Questionnaire (CSQ-8) CSQ-8 (Therapist Version) and Reasons for Termination Checklist Treatment Credibility Questionnaire Treatment Expectations Questionnaire The Treatment History Interview (THI)	The implementation monitoring plan will be guided by 1) critical steps of the Quality Implementation Framework (QIF) ³⁶ ; 2) process evaluation and implementation monitoring outlined by Saunders ¹³⁵ ; and 3) implementation outcomes specified by Proctor. ³⁵ The process evaluation will include both quantitative and qualitative assessments to monitor the implementation activities and address barriers that may arise during the study. The mixed methods will include feedback from the student participants, counseling staff, and directors.
Aim 7. To explore counselor experiences working with suicidal college students. All analyses for this aim will be exploratory. Counselors will	CSQ-8 (Therapist Version) and Reasons for Termination Checklist	Aspects of counselor participants' experiences to be explored include their beliefs about suicide, self-identified theoretical orientation and training

Table 2. CAMPUS Trial Objectives, Endpoints, and Justification

Objectives	Endpoints	Justification for Endpoints
be separated into clinically relevant groups based on cut-points on key demographic variables. Between-group differences on counselor measures will be explored.	Counselor Treatment Expectations Zero Suicide Workforce Survey (abbreviated) Focused Interview Demographic Information Form TAU Questionnaire	experiences, expectations for and satisfaction with providing different types of therapy during the study, and general experiences of participating in the study.
Aim 8: Within each treatment stage, determine whether CAMS produces greater reductions in SR than TAU (Stage 1) and whether CC-DBT produces greater reductions in SR than Continued CAMS (Stage 2).	Scale for Suicidal Ideation (SSI) Self-Injurious Thoughts and Behaviors Interview (SITBI)	The primary outcomes will be reduction in suicidal risk (SR; suicidal ideation primarily but also non-suicidal self-injury, suicide attempts, and suicides) at the end of Stage 1, Stage 2, and at 3-month follow-up. Recognizing that measurement of suicide-related behaviors is fraught with challenges, ¹¹² we are defining SR as “suicidal ideation, attitudes, behaviors and plans which take into account severity, intent, and ability to cope with ideation without engaging in suicidal behaviors, such as planning/rehearsal, non-suicidal self-injury (NSSI), suicide attempts (SAs), and suicide.” Our primary assessment measures for SR are two interviews to measure suicidal ideation (SI; defined as self-reported thoughts of suicide-related behavior) and suicidal behaviors, including suicide attempts and NSSI. Suicides will also be tallied.

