location/preference of the counselor participant. In addition, we are proposing modifications to the overall length of the trial and the treatments to better fit within the CCC setting.

The multisite CAMPUS Trial will enroll moderately to severely suicidal college students in the “emerging adulthood” phase (ages 18-25) seeking services at CCCs and evaluate the relative effectiveness of the adaptive treatment strategies (ATSSs) when delivered via a hybrid model. The four ATSSs will be developed and refined within the context of the current sequential multiple assignment randomized trial (SMART). The SMART will have two stages of intervention. In Stage 1, 480 participants from the participating CCCs will be randomized to 4-6 weeks of: (1) a suicide-focused treatment – Collaborative Assessment and Management of Suicidality (CAMS) or (2) Treatment as Usual (TAU).

Sufficient responders to either intervention will enter the maintenance phase. Non-responders will be re-randomized to one of two Stage 2 higher intensity/dosage intervention options for an additional 1-8 weeks: (1) CAMS (either continued or administered for the first time) or (2) Counseling Center Dialectical Behavior Therapy Dialectical Behavioral Therapy for College Counseling settings (CC-DBT), which includes individual therapy and skills training.

For the CAMPUS Trial, we will also enroll up to 40 CCC counselors who will serve as study counselor participants and periodically complete measures focused on the experience of counselors working with suicidal college students.

Objectives: The overall purpose of the multisite CAMPUS Trial is to evaluate the relative effectiveness of four adaptive treatment strategies (ATSSs) to treat college students who report suicidal ideation when first seeking services at their college counseling center.

The CAMPUS Trial aims to identify which sequence(s) of treatments are most effective on average (average treatment effect or ATE), which treatment sequence(s) are most cost-effective for college counseling centers to provide, and whether outcomes vary based on key student characteristics (heterogeneity of treatment effect or HTE).

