Another aim of the CAMPUS Trial is to assess counselor participants’ experience of participating in the study and providing treatment to suicidal college students, including examining their expectations for therapy and beliefs about suicide. These analyses will be qualitative and exploratory in nature and will not have specified hypotheses.

Endpoints:	
Primary Endpoints/Outcome Measures: The primary endpoint for the CAMPUS Trial is reduction in suicidal risk at the end of Stage 1 treatment, Stage 2 treatment, and at 3-month follow-up. Differences in suicidal risk will be operationally defined as changes in suicidal ideation, non-suicidal self-injury, and suicide attempts, as well as differences in deaths by suicide.
 
Secondary Endpoints/Outcome Measures: Secondary outcomes for the CAMPUS Trial are changes in overall distress, depression, social and generalized anxiety, substance abuse, eating concerns, academic functioning, health care utilization, and student participant ratings of severity and improvement in suicidal risk.

Study Population:	Recruitment of 480 college students (aged 18-25) is the target for randomization to Stage 1 treatments. Up to 40 counselors will also be recruited to participate as study therapists. The number of counselor participants may increase or decrease throughout the project based on turnover, but we expect to maintain approximately 24 participating counselors at any given time across the participating sites in each of the enrollment years.
Phase or Stage:	Phase III Clinical Trial
Description of Sites/Facilities Enrolling Participants:	This multisite study will include the following four primary sites: University of Nevada – Reno, Duke University, University of Oregon, and Rutgers University. Research will be conducted at each site through each College Counseling Center (CCC). The Single IRB will be sponsored and overseen by Duke University. Other CCCs may be added as performance sites in the future to increase enrollment numbers as needed.

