supervision corresponding to the intervention will be tracked using logs of personnel time (and multiplied by corresponding wage and facility overhead rates). To make cost-effectiveness comparisons, incremental cost-effective ratios (ICERs) will be calculated as the incremental cost divided by the incremental clinical benefits (e.g., remission rate of suicide risk) for each pairwise comparison of intervention strategies. Uncertainty surrounding these estimates will be calculated as cost-effectiveness acceptability curves and confidence intervals, using bootstrapping with Monte Carlo simulations. In addition, we will conduct an exploratory analysis of the “hidden costs” to college campuses associated with not providing adequate treatment for students experiencing suicidal ideation and behaviors (e.g., crises on campus, NSSI in residence halls).

Aim 7 analyses focus on the experience of counselors in the study. Given the relatively small sample size, the fact that the same counselors will be administering all treatments, and no *a priori* hypotheses, we regard these analyses as exploratory. Counselors will be divided into clinically relevant groups based on cut-points on key demographic variables (e.g., age, gender, years of overall experience, years of *experience* treating suicidal students, etc.). Analyses of variance will be used to examine differences in continuous outcomes; logistic regression analyses and contingency table analyses will be used to analyze differences in dichotomous outcomes. we will also use effect size benchmarks and descriptive statistics to gauge potentially meaningful effects (e.g., eta-square > .06; odd ratios > 2.0).

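### Aim 7 compares about 24 to 40 counselors in groups formed at unstated cut-points on variables such as years of experience; keeping those variables continuous would use more of the information at no cost in data

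*Combined protocol and SAP*

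**What the plan says.** Table 2 in Section 3 states for Aim 7 that counselors will "be separated into clinically relevant groups based on cut-points on key demographic variables" and that differences between the groups on the counselor measures will be explored. It names no variable.

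Section 9.3.7 gives the examples: "Counselors will be divided into clinically relevant groups based on cut-points on key demographic variables (e.g., age, gender, years of overall experience", followed by years spent treating suicidal students. On method it says "Analyses of variance will be used to examine differences in continuous outcomes"; dichotomous outcomes get logistic regression and contingency tables. Alongside these it will use effect-size benchmarks and "descriptive statistics to gauge potentially meaningful effects (e.g., eta-square > .06; odd ratios > 2.0". It cites the small sample and the absence of prior hypotheses, and says "we regard these analyses as exploratory".

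Neither place gives a cut value, a number of groups, or an analysis that leaves a numeric variable as a number.

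On numbers, the Synopsis says "we will also enroll up to 40 CCC counselors" and "we expect to maintain approximately 24 participating counselors at any given time". Section 8.1 (counselor measures for Aim 7) lists years of clinical experience and years working with suicidal clients on the counselor Demographic Information Form. Age is not in that list.

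**The concern.** Years of experience is a quantity. Once it is cut, all counselors in a group are treated as alike, and two counselors just either side of the cut are treated as different. The analysis then ignores how outcomes vary with experience inside each group. With so few counselors there is little information to spare, and the purpose of an exploratory aim is to pick up leads worth following.

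There is a second, smaller issue. Because the cut values are not stated, they could be fixed after the counselor outcomes have been seen, which leaves room for chance findings.

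**Working it through.** The documents give no power, alpha or precision figure for Aim 7, so there is no stated figure to reproduce.

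**Inputs.** From the documents: n = 24 (active at one time) and n = 40 (maximum enrolled), from the Synopsis; the eta-square benchmark of .06, from Section 9.3.7. Assumed: two-sided 5% test, a linear relation, one value per counselor and, unless stated otherwise, a normal predictor.

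**Step 1. Information kept after grouping.** Relative to a linear analysis, this is the between-group variance of the predictor divided by its total variance. For two groups of a normal variable cut at quantile p it equals φ(z_p)² / [p(1−p)]. At the median: 0.3989² / 0.25 = 0.637 (that is, 2/π), a loss of 36.3%. The plan fixes neither the groups nor the distribution, so the range matters:

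| Predictor | Grouping | Loss |
|---|---|---|
| Normal | median split | 36.3% |
| Normal | 30/70 | 42.4% |
| Normal | 20/80 | 51.0% |
| Normal | equal thirds | 20.7% |
| Normal | quartiles | 13.9% |
| Uniform | median split | 25.0% |
| Uniform | equal thirds | 11.1% |
| Right-skewed (exponential) | median split | 52.0% |
| Right-skewed (exponential) | equal thirds | 35.1% |

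For a normal predictor, a median split leaves the equivalent of 24 × 0.637 = 15.3 or 40 × 0.637 = 25.5 counselors.

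**Step 2. Power at the plan's own benchmark.** An R² of .06 is r = √.06 = 0.245. After a median split the expected eta-square is .06 × 0.637 = .038, and r becomes 0.195. Using Fisher's z, power ≈ Φ(atanh(r)·√(n−3) − 1.96), ignoring the negligible opposite tail:

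- n = 24, continuous: 0.250 × √21 = 1.146; Φ(−0.81) ≈ 21%.
- n = 24, median split: 0.198 × √21 = 0.907; Φ(−1.05) ≈ 15%.
- n = 40, continuous: 0.250 × √37 = 1.521; Φ(−0.44) ≈ 33%.
- n = 40, median split: 0.198 × √37 = 1.204; Φ(−0.76) ≈ 22-23%.

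Simulation agrees to within about a point.

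**Step 3. A larger effect.** At r = 0.5, simulated power is 73% continuous against 51% split at n = 24, and 92% against 75% at n = 40.

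**Step 4. Do three groups rescue it?** Thirds keep more of the between-group variance, but analysis of variance spends a further degree of freedom and does not use the ordering of the groups. Simulated power for equal thirds at r = 0.5 is 48% (n = 24) and 75% (n = 40), about the same as the median split.

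**Step 5. Open cut-points.** If the best of three quartile cuts were reported when there is no true effect, the simulated false-positive rate is about 12.5-13% instead of 5%.

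**The case against.** The strongest reply is that this is a tertiary aim, openly labelled exploratory, with no hypotheses and with its small sample acknowledged. The Synopsis describes the counselor work as qualitative and exploratory. No alpha is stated, so the 5% test is imported. At the plan's own benchmark even the continuous analysis has low power, so most missed associations would be due to the number of counselors and not to grouping. All of this stands and limits the weight of the point. It does not justify the grouping, because the plan does prescribe formal comparisons and the alternative uses the same data.

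A second reply is that the groups are meant to be clinically relevant. Section 5.1 admits trainees as well as employed counselors, so an early-career versus established contrast could be sensible, and a true threshold effect would change the figures. That is fair, but no threshold is given.

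Three stronger readings are tempting and are not supported:

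- A reader might infer that more than a third of the information is lost as a matter of fact. That needs an unfavourable case, such as two groups of a roughly normal variable. The plan does not say two groups, and other choices give losses from about 11% to over 50%.
- A reader might infer that every listed variable could simply be kept continuous. Gender is categorical and loses nothing. Age is not in the listed contents of the counselor form. For experience, Section 8.1 refers to years but does not show whether the item is an open number or in bands.
- A reader might infer that cut-points will be searched. The documents describe no such search; they only leave it open.

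Finally, several Aim 7 measures are repeated per student or every six months (Table 1 notes), so one value per counselor is a simplification.

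**Conclusion.** The point holds as a minor one. Section 9.3.7 prescribes a less efficient method for numeric counselor variables, and a better one is available from the same form. The direction does not depend on whether two or three equal groups are used. The size does depend on assumptions that the plan leaves open: about 36% or more of the information for a two-way split of a roughly normal, linearly related variable, and roughly 11% to over 50% otherwise. In power, the difference is about 6 to 7 percentage points at n=24 and 10 to 11 at n=40 at the plan's benchmark, and 22 (73 − 51) and 17 (92 − 75) points at r = 0.5. These rest on a two-sided 5% test, normality, linearity and one value per counselor. The case is firm for the two experience variables and conditional for age. Aims 1-3 are not affected.

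**What to change.** In Table 2 (Aim 7) and Section 9.3.7, state that years of overall experience and years treating suicidal students will be analysed as continuous predictors, by linear or logistic regression, or by Spearman correlation where skewed. Treat age the same way if it is collected as a number, and confirm that the counselor form records it. Keep group comparisons for truly categorical variables such as gender and theoretical orientation. Use cut-points only in descriptive tables.

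The cost is a change of wording, provided that experience is recorded as a number. The one downside is a linearity assumption, which a scatterplot or a rank correlation would cover.
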